#### APPENDIX 3. UC-PRO/SS Scoring Rules

The Ulcerative Colitis Patient-Reported Outcomes Signs and Symptoms (UC-PRO/SS) is a 9-item daily diary, designed for electronic administration. Patients/respondents are instructed to complete the diary each evening, reflecting back on their experiences "during the past 24 hours." Daily administration is essential in order to capture change in the patient's condition consistent with symptom variability. The UC-PRO/SS takes approximately three minutes to complete.

The UC-PRO/SS yields two separate weekly average scores: Bowel signs and symptoms (6 items) and functional symptoms (3 items). There is no single total score. The weekly scores can be used alone or as part of a profile.

Document \\quintiles.net\enterprise\Apps\sasdata\SASb\SAS\Arena\APD334\RZA28116\Biostatistics\Documenta

tion\SAP\503-Final SAP v2.0\APD334-203\_SAP\_Final v2.0-20231120\_clean.docx

Author: Version Number: 2.0 PPD

[figure not shown]
> Version Date: 20Nov2023

Template No.: CS\_TP\_BS016 Revision 7 Reference: CS\_WI\_BS005

Effective Date: 01Nov2021

Page 63 of 70

Document: \quintiles.net\enterprise\Apps\sasdata\SASb\SAS\Arena\APD334\RZA28116\Biostatistics\Documenta

tion\SAP\503-Final SAP v2.0\APD334-203\_SAP\_Final v2.0-20231120\_clean.docx

Author: PPD Version Number: 2.0

Version Date: 20Nov2023

Template No.: CS\_TP\_BS016 Revision 7 Reference: CS\_WI\_BS005

Effective Date: 01Nov2021

Page 64 of 70

#### 4=Very Severe

#### Derivation:

A daily score is the mean of responses to items for each scale: Bowel signs and symptoms (Questions 1-5 and 7), and functional symptoms (Questions 6, 8 and 9). A weekly average score for each scale is then calculated with no imputation using the mean of at least four out of the seven daily scores. If four or more days of data are missing for any week, the weekly average score for each scale is set to missing for that week.

Document: \\quintiles.net\enterprise\Apps\sasdata\SASb\SAS\Arena\APD334\RZA28116\Biostatistics\Documenta

tion\SAP\503-Final SAP v2.0\APD334-203\_SAP\_Final v2.0-20231120\_clean.docx

Author: PPD Version Number: 2.0

Version Date: 20Nov2023

Template No.: CS\_TP\_BS016 Revision 7 Reference: CS\_WI\_BS005

Effective Date: 01Nov2021

PROTOCOL APD334-203

Statistical Analysis Plan

Page 65 of 70

20Nov2023

#### APPENDIX 4. SF-36 Scoring Rules

The Medical Outcomes Study 36 Item Short Form Health Survey (SF-36) is a 36-item self-administered questionnaire which has 8 scales: Physical functioning (10 items), role limitations due to physical problems (4 items), role limitations due to emotional problems (3 items), vitality (4 items), mental health (5 items), social function (2 items), bodily pain (2 items), and general health perceptions (5 items). Each item response is scored from 0 to 100 and items in the same scale are averaged together to create 8 subscores. Scores range from 0 to 100. A higher score indicates a more favorable health state.

#### The 8 dimensions are defined as:

- Physical functioning: Questions 3 to 12
- Role limitations due to physical problems: Questions 13 to 16
- Role limitations due to emotional problems: Questions 17 to 19
- Vitality: Questions 23, 27, 29, 31
- Mental health: Questions 24 to 26, 28, 30
- Social function: Questions 20, 32
- Bodily pain: Questions 21, 22
- General health perceptions: Questions 1, 33 to 36

Document: \quintiles.net\enterprise\Apps\sasdata\SASb\SAS\Arena\APD334\RZA28116\Biostatistics\Documenta

tion\SAP\503-Final SAP v2.0\APD334-203\_SAP\_Final v2.0-20231120\_clean.docx

Author: PPD Version Number: 2.0

Version Date:

Template No.: CS\_TP\_BS016 Revision 7 Reference: CS\_WI\_BS005

Effective Date: 01Nov2021

PROTOCOL APD334-203

Statistical Analysis Plan

Page 66 of 70

#### APPENDIX 5. CLASSIFICATION OF RESCUE THERAPY

This appendix outlines the algorithm for the Arena clinical team/medical reviewers to classify rescue therapies for ulcerative colitis (UC) in a blinded manner. This will help establish 1) intercurrent events for the efficacy estimands, and 2) whether a subject will be excluded from the Per Protocol Set(s). All rescue therapies identified by the medical reviewers per the algorithm below will be imported in programming. This process will be repeated until database lock and the list of all rescue therapies identified will be finalized before study unblinding.

Only medications and medical procedures reported on the electronic case report forms (eCRFs) can be assessed whether they are rescue therapy for UC. If the exposure happens in the follow-up period (beginning on or after the date of last study treatment administration), then it would not be considered as a rescue therapy.

Biologics with immunomodulatory properties

- Rule:
- Any exposure after first dose
- List of medications
  - Anti-TNFα antibodies:
    - ADALIMUMAB
    - CERTOLIZUMAB
    - CERTOLIZUMAB PEGOL
    - GOLIMUMAB
    - INFLIXIMAB
  - Other Biologics:
    - USTEKINUMAB
    - VEDOLIZUMAB

Non-biologics with immunomodulatory properties

- Immunosuppressants
  - Rules:
    - After first dose and up to and including Week 8: any increase from baseline for more than
       5 days

Document: \quintiles.net\enterprise\Apps\sasdata\SASb\SAS\Arena\APD334\RZA28116\Biostatistics\Documenta

tion\SAP\503-Final SAP v2.0\APD334-203\_SAP\_Final v2.0-20231120\_clean.docx

Author: PPD Version Number: 2.0

Version Date: 20Nov2023

Template No.: CS\_TP\_BS016 Revision 7 Reference: CS\_WI\_BS005

Effective Date: 01Nov2021

Page 67 of 70

- After Week 8: Any dose above baseline
- List of medications
  - MERCAPTOPURINE
  - AZATHIOPRINE
  - TIOGUANINE
  - METHOTREXATE
  - METHOTREXATE SODIUM
- 5-ASA compounds
  - Rules:
    - After first dose and up to and including Week 8: Any increase from baseline for more than 5 days
    - After Week 8: Any dose above baseline
  - List of medications
    - MESALAZINE
    - BALSALAZIDE
    - BALSALAZIDE DISODIUM DIHYDRATE
    - BALSALAZIDE SODIUM
    - OLSALAZINE SODIUM
    - SULFASALAZINE
    - BECLOMETASONE W/MESALAZINE
  - Routes
    - ORAL
    - RECTAL
- Other small molecule immunomodulatory active agents
  - Rules:
    - After first dose and up to and including Week 8: Any increase from baseline (including new use) for more than 5 days
    - After Week 8: Any dose above baseline
  - List of medications
    - CICLOSPORIN
    - TACROLIMUS

Document: \quintiles.net\enterprise\Apps\sasdata\SASb\SAS\Arena\APD334\RZA28116\Biostatistics\Documenta

tion\SAP\503-Final SAP v2.0\APD334-203\_SAP\_Final v2.0-20231120\_clean.docx

Author: PPD Version Number: 2.0

Version Date: 20Nov2023

Template No.: CS\_TP\_BS016 Revision 7 Reference: CS\_WI\_BS005

Effective Date: 01Nov2021

Page 68 of 70

- TOFACITINIB
- TOFACITINIB CITRATE
- Systemic glucocorticoids
  - Systemic glucocorticoids given via oral or rectal routes of administration
    - Rules:
      - After first dose and up to and including Week 8: Any increase from baseline for more than 7 days
      - After Week 8: Any dose above baseline
    - List of medications
      - BETAMETHASONE
      - BETAMETHASONE DIPROPIONATE
      - BETAMETHASONE SODIUM PHOSPHATE
      - DEXAMETHASONE
      - DEXAMETHASONE SODIUM PHOSPHATE
      - DEXAMETHASONE VALERATE
      - METHYLPREDNISOLONE
      - METHYLPREDNISOLONE SODIUM SUCCINATE
      - PREDNISOLONE
      - PREDNISOLONE SODIUM PHOSPHATE
      - PREDNISOLONE METASULFOBENZOATE SODIUM
      - PREDNISONE
      - TRIAMCINOLONE
      - HYDROCORTISONE
      - HYDROCORTISONE ACETATE
      - HYDROCORTISONE BUTYRATE
      - HYDROCORTISONE SODIUM SUCCINATE
    - Routes
      - ORAL
      - RECTAL
  - Systemic glucocorticoids given via parenteral routes of administration
    - Rule:
      - Any exposure after first dose

Document: \quintiles.net\enterprise\Apps\sasdata\SASb\SAS\Arena\APD334\RZA28116\Biostatistics\Documenta

tion\SAP\503-Final SAP v2.0\APD334-203\_SAP\_Final v2.0-20231120\_clean.docx

Author: PPD Version Number: 2.0

Version Date: 20Nov2023

Template No.: CS\_TP\_BS016 Revision 7 Reference: CS\_WI\_BS005

Effective Date: 01Nov2021

Page 69 of 70

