#### 2.5. Estimands

The primary and the secondary estimands to support regulatory decisions are described in Table 1 below. The analyses will be performed on the Full Analysis Set (FAS) with baseline MMS 5-9 as defined in Section 5.3. Supplementary analyses for the primary estimand will be performed on the modified Full Analysis Set (mFAS) and the Per Protocol populations, respectively (ICH 2019). Supplementary analyses for secondary estimands will be performed on the mFAS only. Intercurrent events include: 1) discontinue the study for lack of efficacy or adverse event related to UC, 2) initiate a rescue medication for UC, 3) have an increase in dose over Baseline levels in their existing UC medication, or 4) have a rescue non-drug treatment (eg., colectomy, ileostomy, or sigmoidectomy) before the efficacy assessment. Refer to APPENDIX 5 for the definition of rescue therapies (medication and medical procedures).

Table 1: List of Primary and Secondary Estimands

Estimand	Definition	Attributes			
		Population	Variable/ Endpoint	Intercurrent event handling strategy	Population-level summary measure
Primary Estimand	Efficacy of etrasimod on clinical remission at Week 12	Randomized Japanese participants who receive at least 1 dose of study treatment and with Baseline MMS 5 to 9	The proportion of participants with SF subscore = 0 (or = 1 with a ≥ 1-point decrease from Baseline), RB subscore= 0, and ES ≤ 1 (excluding friability) at Week 12	Participants with any of the 4 intercurrent events a before the efficacy assessment will be treated as nonresponders.	Difference between each etrasimod dose (1 and 2 mg) and placebo in the endpoint at Week 12
Secondary Estimand 1	Efficacy of etrasimod on endoscopic improvemen t at Week 12	Randomized Japanese participants who receive at least 1 dose of study treatment and with Baseline MMS 5 to 9	The proportion of participants with ES ≤ 1 (excluding friability) at Week 12.	Same as the intercurrent event handling strategy for the primary estimand	Difference between each etrasimod dose (1 and 2 mg) and placebo in the endpoint at Week 12
Secondary Estimand 2	Efficacy of etrasimod on symptomatic	Randomized Japanese participants who receive at	The proportion of participants with SF subscore = 0 (or = 1 with $a \ge 1$ -point	Same as the intercurrent event handling strategy	Difference between each etrasimod dose (1 and 2 mg) and placebo in the

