2.0 Author: PPD Version Date: 20Nov2023

Template No.: CS\_TP\_BS016 Revision 7 Reference: CS\_WI\_BS005

Effective Date: 01Nov2021

PROTOCOL APD334-203

Statistical Analysis Plan

Page 15 of 70

Estimand	Definition	Attributes			
		Population	Variable/ Endpoint	Intercurrent event handling strategy	Population-level summary measure
	remission at Week 12	least 1 dose of study treatment and with Baseline MMS 5 to 9	decrease from Baseline) and RB subscore= 0 at Week 12.	for the primary estimand	endpoint at Week 12
Secondary Estimand 3	Efficacy of etrasimod on mucosal healing at Week 12	Randomized Japanese participants who receive at least 1 dose of study treatment and with Baseline MMS 5 to 9	The proportion of participants with ES ≤ 1 (excluding friability) with histologic remission measured by a Geboes Index score < 2.0 at Week 12.	Same as the intercurrent event handling strategy for the primary estimand	Difference between each etrasimod dose (1 and 2 mg) and placebo in the endpoint at Week 12
Secondary Estimand 4	Efficacy of etrasimod on clinical response at Week 12	Randomized Japanese participants who receive at least 1 dose of study treatment and with Baseline MMS 5 to 9	The proportion of participants with a ≥ 2-point and ≥ 30% decrease from baseline in MMS, and a ≥ 1-point decrease from baseline in RB subscore or an absolute RB subscore ≤ 1 at week 12.	Same as the intercurrent event handling strategy for the primary estimand	Difference between each etrasimod dose (1 and 2 mg) and placebo in the endpoint at Week 12
Secondary Estimand 5	Efficacy of etrasimod on endoscopic normalizati on at Week 12	Randomized Japanese participants who receive at least 1 dose of study treatment and with Baseline MMS 5 to 9	The proportion of participants with ES=0 at week 12.	Same as the intercurrent event handling strategy for the primary estimand	Difference between each etrasimod dose (1 and 2 mg) and placebo in the endpoint at Week 12

<sup>a Intercurrent events include: 1) discontinue the study for lack of efficacy or adverse event related to UC, 2) initiate a rescue medication for UC, 3) have an increase in dose over Baseline levels in their existing UC medication, or 4) have a rescue non-drug treatment (eg, colectomy, ileostomy, or sigmoidectomy) before the efficacy assessment. Refer to APPENDIX 5 for the definition of rescue therapies (medication and medical procedures).

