# 3. STUDY DESIGN

#### 3.1. General Description

This is a dose ranging, multicenter, randomized, double-blind, placebo-controlled study to evaluate the efficacy and safety of etrasimod 1 and 2 mg in Japanese participants with moderately to severely active UC. The study consists of a 28 Day Screening Period, a 12 Week Induction Treatment Period, and a 4 Week Follow Up Period. Eligible participants will be randomized (1:1:1 ratio) to receive either etrasimod (1 mg once daily), etrasimod (2 mg once daily), or matching placebo (once daily) in a double-blind fashion for 12 weeks. Randomization will be stratified by (a) naïve to biologic or Janus kinase (JAK) inhibitor therapy at study entry (yes or no), (b) baseline corticosteroid use (yes or no), and (c) baseline disease activity (modified Mayo score [MMS]: 4 to 6 or 7 to 9).

A total of 96 participants are planned to be enrolled in the study, with 32 participants expected in each of the 3 treatment groups. The target subject population will include those who have had an inadequate response to, loss of response to, or intolerance to the following:

- Conventional therapy, and are naïve to biologic or JAK inhibitor therapy
- Biologic or JAK inhibitor (participants in this category may have received prior conventional therapy)

Participant eligibility will be determined during a 4-Week (28-Day) Screening Period. Entry criteria will be based on confirmation of moderately to severely active UC, defined by an MMS of 4 to 9, which includes an ES  $\geq$  2 and rectal bleeding (RB) subscore  $\geq 1$ .

At the end of the 12 Week Induction Treatment Period, participants will undergo Week 12 efficacy and safety assessments and be evaluated for clinical response/remission. Participants will then have the option to enter an open label extension (OLE) study (Study APD334-303) following completion of Week 12 study procedures provided they meet all eligibility criteria for the OLE. Participants must complete Week 12 to be eligible for the OLE.

Participants who discontinue from the study and do not participate in the OLE study will have 2 Week and 4 Week Follow Up visits after the last on treatment visit/Early Termination (ET) visit. The study design is outlined in Figure 1 below.

This study will be early discontinued in agreement with Pharmaceuticals and Medical Devices Agency (PMDA).

\\quintiles.net\enterprise\Apps\sasdata\SASb\SAS\Arena\APD334\RZA28116\Biostatistics\Documenta Document:

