# 16.1.2. Missing Data Methods for Primary Efficacy Variable

Participants who:1) discontinue the study for lack of efficacy or adverse event related to UC (data collected for Primary Reason off Study from End of study eCRF and Adverse Events eCRF), 2) initiate a rescue medication for UC, 3) have an increase in dose over Baseline levels in their existing UC medication, or 4) have rescue non-drug treatment (eg, colectomy, ileostomy, or sigmoidectomy) during the study as confirmed after blinded review by clinical and medical team members before study unblinding will be considered to have a known (ie, non-missing) outcome of nonresponse and not as having missing data in the analysis of all efficacy endpoints at any subsequent timepoints, including the primary endpoint. The rescue therapies will be identified by the Arena clinical team during blinded data review. Refer to APPENDIX 5 for the definition of rescue therapies (medication and medical procedures). In scenarios 2 and 3 above, if a subject has an efficacy measurement collected after the initiation or dose increase from Baseline of UC medication, the observed data will be censored at the time of initiation or dose increase and they will be considered as having a nonresponse. Subjects in all 4 scenarios above may still be included in the respective Per Protocol Set, provided they do not violate other criteria for Per Protocol Set. For example, they will be excluded from the Per Protocol Set if they initiate a prohibited medication before the Week 12 efficacy assessment that can affect efficacy of the study treatment and the indication is unrelated to UC.

Document: \\quintiles.net\enterprise\Apps\sasdata\SASb\SAS\Arena\APD334\RZA28116\Biostatistics\Documenta

tion\SAP\503-Final SAP v2.0\APD334-203 SAP Final v2.0-20231120 clean.docx

Author: PPD Version Number: 2.0

Version Date: 20Nov2023

Template No.: CS\_TP\_BS016 Revision 7 Reference: CS\_WI\_BS005

Effective Date: 01Nov2021

Page 35 of 70

Analysis visits will be mapped as per Section 6.4 before any missing data imputation method is applied.

Participants with a missing efficacy outcome will be included in the primary analysis using single imputation as non-responder.

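### SAP Appendix 5 stops classifying rescue at the last dose of study treatment, while the estimand and SAP 16.1.2 run to the efficacy assessment, leaving a narrow gap in the nonresponder rule

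*SAP*

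**What the plan says.** **Estimand (SAP 2.5, Table 1).** Participants with any of four intercurrent events "before the efficacy assessment will be treated as nonresponders". Event 2 is starting a rescue medication for UC. Event 4, in the table footnote, is to "have a rescue non-drug treatment (eg, colectomy, ileostomy, or sigmoidectomy) before the efficacy assessment". The section refers to Appendix 5 for what counts as rescue.

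**Handling (SAP 16.1.2).** The same four events, during the study, give a known nonresponse. If efficacy is measured after a medication start or dose increase, "the observed data will be censored at the time of initiation or dose increase and they will be considered as having a nonresponse". This section also refers to Appendix 5, and it states no last-dose limit.

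**Definition (SAP Appendix 5).** The classification feeds both the intercurrent events and the Per Protocol exclusions: "All rescue therapies identified by the medical reviewers per the algorithm below will be imported in programming". Biologics, parenteral glucocorticoids and the listed procedures count on "Any exposure after first dose". The other drug classes have a minimum duration up to Week 8 and then "After Week 8: Any dose above baseline". Ahead of these rules stands a general cut-off: if "exposure happens in the follow-up period (beginning on or after the date of last study treatment administration), then it would not be considered" rescue.

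**Where follow-up begins.** SAP 3.1 gives participants who discontinue and do not enter the extension study "Follow Up visits after the last on treatment visit/Early Termination (ET) visit". Protocol 6.7.3 allows treatment of a flare once study drug has stopped and the Week 12/ET visit has taken place. Protocol 9.5 counts the follow-up visits from the last administration of study treatment.

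**The concern.** The estimand and the handling rule set the boundary at the assessment. The definition that both rely on sets it at the last dose. Because the list made under Appendix 5 is what enters the programs, the narrower boundary is the one that operates.

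If a UC agent or procedure is newly started between the two dates, it is missing from the list, so neither event 2 nor event 4 is triggered. A remission or endoscopic response seen afterwards then counts for the arm. That contradicts the nonresponder strategy stated for the primary estimand and all five secondary estimands.

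**Working it through.** The plan gives no figure on this point. The check compares the texts and then does study-day and proportion arithmetic.

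**1. Boundaries side by side**

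| Place | Rescue counts until |
|---|---|
| SAP 2.5, Table 1 | the efficacy assessment |
| SAP 16.1.2 | during the study; data after initiation are censored |
| SAP Appendix 5 | the day before the last dose |
| Protocol 10.4 | no explicit last-dose limit; also allows handling by per protocol analysis |

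**2. Can the assessment fall after the last dose?** Inputs: the Week 12 window for endoscopy-based endpoints is Day 66 to 113, or to 141 if affected by COVID-19 (SAP 6.4, Table 2); scheduled, unscheduled and ET visits are all eligible (SAP 6.4); the ET visit is due within 7 days of the last dose and before any new treatment (Protocol Table 6, footnote b).

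- Earliest last dose for which an on-time ET endoscopy can fall in the window: 66 − 7 = Day 59. That is 59 − 57 = 2 days after the scheduled Week 8 visit.
- Room left by the window after a last dose on Day 85: 113 − 85 = 28 days, or 141 − 85 = 56 days if affected by COVID-19.
- Protocol 5.1 foresees ET visits 2 weeks or more, and 4 weeks or more, after the last dose, so the interval is not strictly capped at 7 days.

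The gap can therefore be reached.

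**3. What a case requires.** All of the following must hold:

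- a new agent or procedure begins on or after the last-dose date and before the assessment, which normally departs from Protocol 6.7.3 and Table 6 footnote b;
- it is newly started, because event 3 (a dose increase in existing UC medication) is not worded as rescue;
- event 1 (leaving the study for lack of efficacy or a UC-related adverse event) does not apply;
- there is an in-window endoscopy and no usable one nearer Day 85, since SAP 6.4 takes the closest;
- the participant meets the response definition.

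**4. Size of one reclassification.** Shift in an arm's rate = 100/n percentage points.

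- Planned n = 32 (SAP 7): 100/32 = 3.1.
- SAP 7 says that the actual sample will be smaller but gives no number, and SAP 16.1.3 restricts the primary set to baseline MMS 5 to 9. For assumed n of 24, 16 or 10 the shift is 4.2, 6.3 or 10.0.

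Illustration near the planned rates: 0.315 × 32 = 10.1, taken as 10; 0.05 × 32 = 1.6, taken as 2. The SAP names no interval method, so a Wald interval is assumed: d ± 1.96 × √[p₁(1−p₁)/32 + p₂(1−p₂)/32].

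| 2 mg vs placebo | Difference, points (95% CI) |
|---|---|
| 10/32 vs 2/32 | 25.0 (6.9 to 43.1) |
| 9/32 vs 2/32 (one 2 mg responder reclassified) | 21.9 (4.2 to 39.6) |
| 10/32 vs 1/32 (one placebo responder reclassified) | 28.1 (11.0 to 45.3) |

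These figures describe any single reclassification, whatever its cause. They give the scale and do not measure this gap.

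**The case against.** The strongest reply is that Appendix 5 excludes exposure in the follow-up period, and that the protocol makes this harmless. Flare treatment may start only after study drug has stopped and the Week 12/ET visit has been held, and the ET visit comes before any new treatment. When that order is kept, any new agent after the last dose is also after the assessment, and all the passages agree. SAP 3.3 lists no change to the timing of rescue, and reviewers confirm the events blinded.

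Most of this stands, and it is why the point is narrow. It does not close the gap. The windowing rules in SAP 6.4 do not enforce the visit order, and an intercurrent-event rule has to cover departures from it. Nor does the text settle where follow-up begins: Appendix 5 names the last-dose date, Protocol 9.5 times follow-up visits from the last administration, and SAP 3.1 and Protocol 6.7.3 use the visit. The Per Protocol rescue criterion relies on the same Appendix 5 definition. The general deviation review in SAP 5.4 could still remove a case, but the Per Protocol analysis covers the primary endpoint only (SAP 16.2, Table 3).

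A reader might go further and infer three things that the documents do not support:

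- **That the cut-off is a second defect because it overrides Appendix 5's own class rules.** A rule for any exposure after first dose has no upper end, so some end-point is needed. The fault is where it was placed.
- **That a new agent could have been in use for at most 7 days at the endoscopy.** This assumes a site that breaks one half of footnote b and keeps the other, and late ET visits are foreseen.
- **That so short an exposure would produce a remission.** The documents do not show this. The diary days used for the symptom scores also precede bowel preparation (Protocol 9.4.2), which shortens the time further.

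**Conclusion.** The inconsistency is real and its severity is minor to moderate. Followed literally, Appendix 5 can leave a participant as a responder whom SAP 2.5 and 16.1.2 would make a nonresponder. This rests on reading the parenthesis in Appendix 5 as written and on a departure from the expected visit order under the conditions listed above.

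The documents do not allow the number of such participants to be derived. They also do not show which arm would gain, so a reader who infers bias in favour of etrasimod goes beyond them. With hypothesis testing removed (SAP 3.3 and 6.5), no error rate is at stake. The effect is confined to the reported proportions, differences, odds ratios and intervals.

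**What to change.** Before unblinding, and for outcome classification only, reconcile Appendix 5 with SAP 2.5 and 16.1.2 by replacing the last-dose sentence with the estimand's own boundary, for example:

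*A qualifying exposure that starts before the last component of the efficacy assessment used for an endpoint (diary, endoscopy or biopsy, PGA, or EIM examination, where the endpoint uses them) is rescue therapy for that endpoint, regardless of the date of last study treatment. An exposure that starts after it is not.*

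The PGA and EIM examination are named because SAP 16.3.2 applies the same handling to exploratory endpoints that use them. An agent started between the diary days and the endoscopy would then count for clinical remission but not for symptomatic remission. If the sponsor prefers one boundary for all endpoints, stating that the follow-up period begins after the Week 12/ET efficacy assessment would also remove the conflict.

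The drug-class rules and patient management stay as they are. The cost is one sentence of SAP text. Therapies reported on the eCRF are already classified blinded, so no new data are needed. The downside is possibly a few more nonresponders.
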